The proposal is to investigate the effects of 2 mo of CPAP on EE and EI in obese patients with OSAS. The proposal is a combined ambulatory and laboratory-based study. Free-living measures of physical activity (via waist-actigraphy), food intake (via 3-d food log), sampling of blood for appetite-regulating hormones (leptin, ghrelin, adiponectin, glucagon-like peptide-1 [GLP-1]), lipid profile, and inflammatory markers, and body composition measurements will be obtained at baseline and after 2 mo of CPAP treatment. At the start and conclusion of each treatment phase, patients will enter the laboratory for measures of polysomnographic sleep, hunger levels, and food intake (via ad libitum test meals). The objective of the proposed study is to determine how CPAP treatment affects energy balance in obese OSAS patients. The central hypothesis is that CPAP treatment will improve sleep architecture, which will be associated with improved EE, EI, cardiovascular health, and body composition. We have shown that adverse changes in sleep are associated with alterations in both EE and EI (6, 7). Specifically, reduced sleep duration is associated with increased nocturnal and 24-h EE (6). Moreover, we observed that rapid eye movement (REM) sleep is inversely related to hunger, and that both REM sleep and slow wave sleep (SWS) are inversely related to intake of fat and carbohydrate (7).

Aim 1 (Cardiovascular health): To determine the effects of 2 mo of CPAP compared to pretreatment baseline on body composition in obese OSAS patients.

Hypothesis 1: CPAP will reduce blood pressure, fasting glucose, total cholesterol, inflammatory markers, and percent body fat relative to baseline.

Aim 2 (Energy intake): To determine the effects of 2 mo of CPAP compared to pre-treatment baseline on hunger, food intake, and the hormonal regulation of food intake in obese OSAS patients.

Hypothesis 2: Hunger levels and ad libitum food intake will be lower in patients after CPAP vs. baseline.

Hypothesis 43: Abnormally high leptin levels will be reduced in CPAP vs. baseline. Levels of ghrelin (hunger signal) will be reduced, and glucagon-like peptide-1 (GLP-1; satiety signal) increased, after CPAP vs. baseline.

Research Strategy

Significance

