Study participants: Men and women, age 18-65 y, will be included in the study. Participants will be overweight, with a BMI \geq 25 kg/m2. However, in order to exclude patients who are at the highest risk patients with an AHI > 50 will be excluded from participation (45). Patients will not currently, or have previously been treated with CPAP. Once a diagnosis of OSAS is made and a CPAP prescription is given, but before the start of CPAP treatment, we will meet with potential participants to inform them of the study details. Those interested will begin the screening phase, followed by enrollment if they are eligible and interested in participation. A second group of participants who are diagnosed with OSA but do not choose to undergo CPAP will be studied, as a control group.

Participants will be excluded if they are currently taking any anti-psychotic medications, or hypnotics and other drugs to treat insomnia. Individuals with uncontrolled severe (stage 2) hypertension (blood pressure > 160/100 mmHg) or anemia will be excluded. Participants with uncontrolled severe hypertension will be considered as individuals with known severe hypertension who are not actively receiving medical or drug treatment to manage this disorder. Anemia will be defined from medical history. Habitual drivers, commercial drivers and individuals with any recent near-miss or prior car crashes due to excessive daytime sleepiness (i.e. high-risk drivers) will be excluded. Premenopausal women will be studied in the laboratory during the follicular phase of their menstrual cycle, to exclude the possible confounding effects of sex hormones on outcome parameters like sleep, EE, hunger, and food intake. Participants will be excluded if they have a history of coronary artery disease, transient ischemic attack, or stroke.

Study Design Overview: This study will investigate the effects of CPAP on EE and EI in obese patients with moderate-to-severe OSA and EDS. Following pre-experimental baseline measures, including a 1-d inpatient testing period at the CTSA at Columbia University Medical Center, participants will be instructed to use CPAP at home each night throughout the 2 mo treatment phases. After the 2 mo treatment phase, participants will undergo a repeat of baseline procedures including assessments and the 1-d inpatient testing period. Procedures for the non-CPAP control participants will be the same, with the exception that they will not be using CPAP during the 2-mo period.

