Patients will have a fixed sleep episode from 2300-0700 h during the in-laboratory testing day, which will be identical in both phases. At the baseline visit, no CPAP will be used during the sleep episode. At the 2-mo post-treatment follow-up, CPAP will be used. Overnight sleep will be recorded via PSG during the sleep episode in the laboratory using a portable sleep system. The recording montage will include electroencephalogram, electrooculogram, electromyogram, electrocardiogram, nasal and oral airflow via thermistor, and oxygen saturation via pulse oximetry, and 30-sec epochs of sleep will be scored for sleep staging (Stage 1, Stage 2, SWS,

REM sleep), wakefulness, arousals, and respiratory events according to standard criteria (67). Patients will be discharged after awakening from the laboratory sleep episode.

Upon completion of the baseline 1-d inpatient visit, patients will return home for the 2 mo treatment phase where they will be using CPAP each night. Patients will be instructed to begin to CPAP at home each night throughout the 2 mo treatment phases. Nightly duration of CPAP use will be objectively monitored with a memory chip, and compliance will be defined as the use of the CPAP machine for at least 4 h/night for \geq 70% of the nights (i.e. 64 nights) (55). Participants will also complete a daily CPAP compliance form, in which they will document the duration of CPAP use for the prior night. We will also do random checks of compliance during the 2 mo period. Only compliant patients will undergo the in-lab testing at the end of the intervention period. During the final week of the intervention phase, free-living ambulatory measures of PA (waist-actigraphy), food intake (3-d food log), and subjective (sleep-wake log) and objective (wrist-actigraphy) sleep will be taken, as described above. In-lab testing will be done with the CPAP equipment. At the conclusion of the 2-mo treatment phase, all study procedures and measurements will be repeated. This will include questionnaires, fasting blood sample, anthropometry including BodPod, and the 1-d inpatient period. Procedures for the non-CPAP patients will be same during ambulatory and lab visits. The non-CPAP patients will not use any CPAP during the intervening 2-mo period.

Statistical Procedures:

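### The CPAP compliance threshold restates 70% of the nights in a 2-month phase as 64 nights, more than the phase contains

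*Combined protocol and SAP*

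**What the plan says.** The compliance definition is in Experimental Procedures. A compliant patient uses the machine for at least 4 hours a night on at least "70% of the nights (i.e. 64 nights"). The count is introduced as a restatement of the percentage, not as a second criterion.

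The phase length is 2 months throughout:

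- Specific Aims: "The proposal is to investigate the effects of 2 mo of CPAP on EE and EI in obese patients with OSAS".
- Study Design Overview: "participants will be instructed to use CPAP at home each night throughout the 2 mo treatment phases".
- Experimental Procedures: "patients will return home for the 2 mo treatment phase where they will be using CPAP each night", and on monitoring, "We will also do random checks of compliance during the 2 mo period".
- Statistical Procedures also refers to a 2-month experimental phase.

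None of these places gives a number of days or nights, or describes a longer phase.

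The definition has a direct consequence, also in Experimental Procedures: "Only compliant patients will undergo the in-lab testing at the end of the intervention period".

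**The concern.** A count offered as the equivalent of a percentage has to agree with it. Here the count appears to be larger than the total number of nights to which the percentage applies.

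This matters because the definition is a gate. The final laboratory day provides the second half of each CPAP patient's in-laboratory pair: polysomnography, ad libitum energy intake and the hourly appetite ratings. Statistical Procedures names hunger and energy intake as the main outcomes and analyses the laboratory data by paired t-tests and repeated-measures ANOVA. A CPAP patient who does not reach the second laboratory day contributes no pair to those analyses. If the percentage and the count give different answers, the document does not determine who is analysed, and a reader of the results cannot tell which rule selected the patients.

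**Working it through.** **Inputs.** Threshold share 70% and printed count 64 nights (Experimental Procedures). Phase length 2 months (Specific Aims, Study Design Overview, Experimental Procedures, Statistical Procedures). The number of nights in 2 months is not given and must be assumed. Two consecutive calendar months contain 59 to 62 nights; a wider range of 8 to 9 weeks is 56 to 63 nights.

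**Step 1: try to reproduce 64.** Solve 0.70 × N = 64, so N = 64 / 0.70 = 91.4 nights. In whole nights, 0.70 × 91 = 63.7 and 0.70 × 92 = 64.4. The result is 64 for N = 91 if rounded up, for 91 or 92 if rounded to the nearest, and for 92 if rounded down. A 90-night phase gives 63.0. The printed figure therefore belongs to a phase of about 3 months.

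**Step 2: apply 70% to a 2-month phase.** Nights required = 0.70 × N, rounded up because the rule is a minimum.

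| Assumed nights N | 0.70 × N | Nights required | 64 minus required | 64 / N |
|---|---|---|---|---|
| 56 (8 weeks) | 39.2 | 40 | 24 | 114.3% |
| 59 | 41.3 | 42 | 22 | 108.5% |
| 60 | 42.0 | 42 | 22 | 106.7% |
| 61 | 42.7 | 43 | 21 | 104.9% |
| 62 | 43.4 | 44 | 20 | 103.2% |
| 63 (9 weeks) | 44.1 | 45 | 19 | 101.6% |

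The last column exceeds 100% in every row, so 64 nights cannot be accumulated within the phase. The printed count is 19 to 24 nights above the 70% requirement, or 42% (64 / 45) to 60% (64 / 40) higher.

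**Step 3: other readings.** Rounding cannot close a gap of 19 nights or more. The document sometimes writes treatment phases in the plural, but two 2-month phases would be 118 to 124 nights, and 70% of that is 82.6 to 86.8, or 83 to 87 whole nights, not 64.

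**Step 4: consequence for the gate.** In a phase of 63 nights or fewer, a patient who meets 70% passes on the percentage and fails on the count. Read literally, the count admits no CPAP patient to the final laboratory day.

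**The case against.** The strongest reply is that the percentage is the operative rule and the parenthesis only a gloss. The percentage is complete in itself, can be measured from the device's memory chip, and applies to a phase length stated consistently. A count larger than the phase is visibly a slip, and staff are unlikely to have excluded everyone because of it. This stands as a limit on the likely harm, which is confusion or inconsistent application rather than an empty CPAP group. It does not make the figure right.

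A second point is that follow-up may fall later than 63 nights for some patients. Premenopausal women are to be studied in the laboratory in the follicular phase (Study participants), so a visit could be delayed. If CPAP continued until then and those nights counted, such a patient could reach 64. The document does not say whether they count. This confines the statement about impossibility to phases of 63 nights or fewer; it does not make 64 equal to 70% of 2 months.

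Third, much of the data is not clearly behind the gate. The follow-up food log, activity and actigraphy are free-living measures from the final week of the intervention, so food-log energy intake may be available whatever the compliance result. The fasting blood sample is listed apart from the laboratory day in the account of the repeated procedures: "This will include questionnaires, fasting blood sample, anthropometry including BodPod, and the 1-d inpatient period". Leptin, which drives the sample size, is therefore not clearly gated. The control group is not affected: "The non-CPAP patients will not use any CPAP during the intervening 2-mo period". All of this stands. What is clearly gated is in-laboratory energy intake, hourly hunger and appetite ratings, and polysomnography.

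**Conclusion.** The concern holds. The night count contradicts the percentage and the phase length beside it. The conclusion rests on reading 2 months as 56 to 63 nights, and it is the same at every value in that range. That 64 fits about 91 or 92 nights suggests a figure carried over from a longer phase, but the document does not say so and this is only an inference.

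The point should be fixed because the definition decides which CPAP patients supply in-laboratory data on the main outcomes. It does not undermine the design: the percentage is usable alone, and the effect is confined to the in-laboratory measurements in the CPAP group.

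**What to change.** In Experimental Procedures, reconcile the percentage, the night count and the phase length so that they express one threshold, and state the phase length in nights. If 70% and a 2-month phase are what the sponsor intended, delete the parenthetical count or replace it with one that agrees with the stated number of nights. Which element to keep is for the sponsor to decide. If CPAP patients have already been admitted to, or kept from, the final laboratory testing, record which threshold was applied and report it with the results.

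If the percentage and the 2-month phase stand, this is a one-line correction with no effect on sample size or procedures. If the count was the intended element, the phase length or the percentage would have to change, with the procedures that depend on it, and the cost would be correspondingly larger.

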During the baseline assessment before treatment, patients will enter the laboratory at the CTSA at Columbia University for a 1-d period. Patients will arrive at ~0900 h and will remain in the laboratory for the following 24h. Patients will fill out questionnaires assessing their level of sleepiness during their wake episode throughout the laboratory day. A Likert scale will assess current energy level each hour spent awake ("How energetic do you feel right now?"; "How sluggish do you feel right now?") and a Likert scale will assess current feelings of hunger ("How hungry do you feel right now?"), satiety ("How satisfied do you feel right now?"; "How full do you feel right now?"), and appetite/food preferences ("How much would you like to eat something sweet right now?"; ("How much would you like to eat something salty right now?"; ("How much would you like to eat something savory right now?"; How much would you like to eat fruits/vegetables right now?").

Ad libitum EI will be measured during the laboratory day for each treatment phase. During the laboratory day, participants will self-select their food intake. Participants will have access to a specified food budget for the day (up to \$55.50) to purchase foods and beverages of their choice. Participants will be escorted by study personnel to local markets where they will be able to purchase foods they want to eat during the day. Participants will also have the opportunity to purchase food from take-out restaurants throughout the day. The only restrictions that will be imposed are that nutrient information must be available for the items purchased and that beverages must be nonalcoholic. Participants will not be able to keep any food not consumed during the experimental day. Participants will not be allowed to take any purchased foods home with them. Energy and macronutrient intakes will be calculated using Diet Analysis Plus Software using the weight (pre – post intake) and nutritional information of the food consumed.

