Sample size estimates are for paired-samples, two-tailed level of significance at 0.05 and 80% power, and are based on prior studies showing a significant effect of CPAP vs. baseline on outcomes of interest. We hypothesize that reduced sleepiness in response to active CPAP treatment will result in increased free-living PA compared to sham. We expect to be able to detect an effect size of 1.195 for decreased Stanford Sleepiness Scores (37) with 8 patients. The main outcomes hunger and EI, have not previously been investigated in response to CPAP. However, we have previously demonstrated a relationship between REM sleep and SWS with hunger and food intake (7). We expect to be able to detect an effect size of 1.01 for REM sleep increases (43) and 1.64 for SWS increases (43) with 10 and 6 patients, respectively. We expect to be able to detect an effect size of 0.736 for decreased leptin with 17 patients (62). To have power to detect changes in leptin, we will recruit 25 patients, assuming a 30% drop-out rate.

Change-from-baseline will be calculated for single-measure parameters that are assessed at the pre-experimental baseline, and after the 2-mo experimental phase (including ESS, FOSQ, PA, blood samples, body composition, blood pressure). Paired-samples t-tests will be used to compare single-measure parameters that are assessed during laboratory phase 1 and laboratory phase 2. These will include polysomnographic sleep measures (sleep stages and indices of sleep-disordered breathing), and total energy and macronutrient intakes. Repeated or continuously measured parameters taken during laboratory phase 1 and laboratory phase 2 will be analyzed with two-way repeated measures ANOVA (factors: condition x time). These will include hourly measures of sleepiness (SSS), and appetite-satiety ratings. Non-parametric equivalent tests will be used if data are deemed to be not normally distributed. Significance will be set at p<0.05.

References:

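### Only compliant CPAP patients have the 2-month lab day, by a threshold of 64 nights that exceeds the 2-month phase; the hypotheses and analysis do not carry the restriction through

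*Combined protocol and SAP*

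**What the plan says.** The Experimental Procedures define compliance as at least 4 hours of CPAP per night on at least "70% of the nights (i.e. 64 nights"), in a treatment phase described throughout as 2 months. They then add: "Only compliant patients will undergo the in-lab testing at the end of the intervention period". Later in the same paragraph comes a sentence with no compliance condition: "At the conclusion of the 2-mo treatment phase, all study procedures and measurements will be repeated". It is followed by a list that includes questionnaires, fasting blood, anthropometry and the inpatient day.

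The lab day carries these measures:

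- Intake: "Ad libitum EI will be measured during the laboratory day for each treatment phase".
- Hourly ratings of energy, hunger, satiety and food preference, and sleepiness questionnaires.
- Overnight polysomnography (PSG). For the follow-up night the text says "At the 2-mo post-treatment follow-up, CPAP will be used".

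The ambulatory measures are described separately, with no compliance condition: "During the final week of the intervention phase, free-living ambulatory measures of PA (waist-actigraphy), food intake (3-d food log"). The non-CPAP controls have the same ambulatory and lab visits without CPAP.

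Hypothesis 2 reads: "Hunger levels and ad libitum food intake will be lower in patients after CPAP vs. baseline". The Statistical Procedures call hunger and energy intake the main outcomes and state: "Paired-samples t-tests will be used to compare single-measure parameters that are assessed during laboratory phase 1 and laboratory phase 2". Hourly ratings are to be analysed by repeated measures ANOVA. No analysis set is named, and nothing is said about CPAP patients without a second lab phase.

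**The concern.** Two things need attention.

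First, the rule that decides who has the second lab day contradicts itself. Its percentage and its night count cannot both hold in a 2-month phase.

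Second, entry to the second lab day depends on behaviour after baseline. A CPAP starter below the threshold has no second-phase value for intake, hourly ratings or PSG, by rule and not by chance. The paired comparisons in the CPAP group can then include compliers only, whereas Hypothesis 2 speaks of patients after CPAP in general. Controls are not selected in this way, so any comparison with them would set selected CPAP patients against unselected controls.

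At stake is how the main outcomes are read. If patients who use CPAP regularly also change their eating more (or less) for other reasons, the complier estimate will not equal the effect in all who start CPAP. Lab data not collected at 2 months cannot be recovered later.

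**Working it through.** **1. The threshold.** The inputs are 70% and 64 nights, from the Experimental Procedures. The length of two consecutive calendar months, 59 to 62 nights, is my assumption. Nights required = 0.70 × nights, rounded up because the rule says at least.

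| Nights in phase | 0.70 × nights | Whole nights required | 64 as share of phase |
|---|---|---|---|
| 59 | 41.3 | 42 | 108% |
| 60 | 42.0 | 42 | 107% |
| 61 | 42.7 | 43 | 105% |
| 62 | 43.4 | 44 | 103% |

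In reverse, 64 / 0.70 = 91.4 nights, about 3 months. The stated count does not reproduce for a 2-month phase, and read literally it could not be met.

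**2. The sample size.** The inputs, from the Statistical Procedures, are a paired design, two-sided 0.05, 80% power, effect size 0.736 for leptin and 30% drop-out. The exact paired t-test (noncentral t) gives 81.3% power with 17 patients and 78.6% with 16, so 17 is right. Recruitment: 17 / (1 − 0.30) = 24.3, rounded up to 25. Both stated figures hold.

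**3. How many CPAP patients reach the second lab day.** This depends on whether the 30% includes non-compliers, which the plan does not say.

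- If it does, 17 remain.
- If it does not, 25 × 0.70 = 17.5 patients remain before non-compliance. With assumed non-compliance of 10, 20 or 30%, 17.5 × 0.9 = 15.75, 17.5 × 0.8 = 14.0 and 17.5 × 0.7 = 12.25, that is 15, 14 or 12 whole patients.

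The plan gives no power calculation for hunger or intake. For a paired t-test on lab intake, the change detectable with 80% power is 0.72 SD with 17 tested, and 0.78, 0.81 and 0.89 SD with 15, 14 and 12.

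**4. Size of a possible selection bias.** The documents give neither the correlation r between compliance and change nor the non-compliance rate; both are assumed. In the simulation (200,000 trials per cell), change is standard normal with no true effect, a compliance score has correlation r with change, the k highest of n are tested, and a two-sided t-test is run at 0.05. Each cell shows bias in SD, then type I error.

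| Tested | r = 0 | r = 0.1 | r = 0.3 | r = 0.5 |
|---|---|---|---|---|
| 15 of 17 | 0; 5.0% | 0.02; 5.1% | 0.06; 5.8% | 0.10; 7.3% |
| 14 of 17 | 0; 5.0% | 0.03; 5.2% | 0.09; 6.4% | 0.15; 9% |
| 12 of 17 | 0; 5% | 0.05; 5.3% | 0.14; 7.6% | 0.23; 13% |
| 17 of 25 | 0; 5.0% | 0.05; 5.5% | 0.15; 9.6% | 0.25; 19% |

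The last row takes the whole 30% drop-out to be non-compliance. A large-sample check for that row uses bias = r × φ(z) / 0.68, where 17/25 = 0.68 and φ(z) / 0.68 is about 0.53. At r = 0.5 this gives 0.26, slightly above the simulated 0.25 because the sample is small. A negative r gives the same sizes in the opposite direction.

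**The case against.** The strongest reply is that the restriction is stated openly and serves the purpose of the study. The central hypothesis runs through improved sleep architecture, so an estimate in patients who actually used CPAP is a defensible mechanistic target, and bias exists only relative to an all-starters effect that the plan never adopts. This largely stands. A reader might infer that the plan conceals the selection; it does not. What is missing is narrower: the hypothesis and the analysis section do not carry the restriction through to an analysis set or a label.

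The sentence about repeating all procedures can fairly be read as a list of what the follow-up contains, so it calls for clarification and is not a contradiction of the same weight as the night count.

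A reader might also infer that every 2-month outcome is limited to compliers. The documents do not support that. The food log and activity measures in the final week carry no compliance condition (no test is named for the food log). For the change-from-baseline outcomes (sleepiness and quality-of-life questionnaires, activity, blood, body composition, blood pressure) the text is unclear.

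Nor do the documents show that the lab results will be biased. With r = 0 there is no bias, and at r = 0.1 type I error stays within about half a percentage point of nominal.

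Finally, it is tempting to demand lab testing of every CPAP starter. That is a trade-off: it adds inpatient stays and dilutes the estimate, and because CPAP is used on the follow-up night, the PSG of a low user would partly reflect that one night.

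**Conclusion.** The point holds in two parts. The compliance threshold is wrong as written: 70% of a 2-month phase is 42 to 44 nights, while 64 nights is 103 to 108% of that phase and matches about 91 nights. The documents do not show which element is in error. Separately, the second-phase lab results in the CPAP group describe compliers only, the controls are not so restricted, and neither Hypothesis 2 nor the Statistical Procedures says so.

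The consequence for the estimates is conditional. Relative to all CPAP starters, bias ranges from zero, if compliance is unrelated to change, to about 0.25 SD with type I error near 19% at the most extreme combination examined. These sizes rest on assumed correlations and non-compliance rates and are illustrations, not predictions. The concern does not extend to the sample size: 17 evaluable and 25 recruited are arithmetically correct. The Statistical Procedures specify no test against controls, so the imbalance between groups matters only if such a comparison is made.

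This should be corrected. It does not invalidate the lab results for compliers.

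**What to change.** 1. Reconcile the 70% rule, the 64-night count and the 2-month phase before the rule is applied. State which 2-month measures the compliance condition covers, given the sentence that all procedures will be repeated.
2. Label the CPAP-group lab-phase results, and the conclusion for Hypothesis 2, as applying to compliers only. Do not present them as the effect in all patients who start CPAP. If they are set beside the controls, say that only the CPAP group was selected on compliance.
3. Commit to reporting the number of CPAP starters not tested at 2 months, by reason, with their baseline values.
4. State whether the 30% drop-out includes non-compliers.

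These changes cost protocol and analysis wording and a short reporting table, with no added patients or visits.

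The sponsor may also weigh attempting the 2-month lab day in all CPAP starters, with an all-starters estimate and confidence interval beside the labelled complier result. Among 17 patients this means about 2, 3 or 5 extra 24-hour stays with PSG (17 − 15, 17 − 14, 17 − 12 at the assumed 10, 20 and 30% non-compliance), each with a food budget of up to $55.50. It also dilutes the estimate. Intake has no planned effect size, so the plan's leptin value of 0.736 serves as an illustration. If a share q of patients does not comply and does not change, the effective size is 0.736(1 − q) / √(1 + q(1 − q) × 0.736²) = 0.647, 0.565 and 0.488, and power with 17 is about 71, 59 and 47%. If this option is taken, the protocol should say how the PSG of low users is to be interpreted.

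### The hourly hunger, appetite and sleepiness ratings go to a repeated-measures ANOVA with no sphericity correction and no rule for missing ratings. The hunger test itself keeps its 5% error rate, but the interaction test and the number of patients analysed are unprotected.

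*Combined protocol and SAP*

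**What the plan says.** Statistical Procedures sends parameters measured repeatedly during the two laboratory days to "two-way repeated measures ANOVA (factors: condition x time", and adds: "These will include hourly measures of sleepiness (SSS), and appetite-satiety ratings". Significance is p<0.05. The only fallback is a non-parametric equivalent if the data are judged non-normal. The section gives no sphericity test or correction, no covariance structure and no handling of a missing rating. It does not say which ANOVA term decides the hunger question.

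The same section calls hunger and energy intake the main outcomes. Hypothesis 2 in Specific Aims predicts lower hunger after CPAP than at baseline.

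On timing, Experimental Procedures says: "A Likert scale will assess current energy level each hour spent awake". The hunger, satiety and food-preference items follow in the same sentence. Patients arrive at about 0900 h and the sleep episode starts at 2300 h.

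The sample size is for "paired-samples, two-tailed level of significance at 0.05 and 80% power" and is driven by leptin: "effect size of 0.736 for decreased leptin with 17 patients (62". The plan then states "we will recruit 25 patients, assuming a 30% drop-out rate". No effect size is given for hunger.

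**The concern.** Ratings taken an hour apart in the same person, around meals, are likely to be serially correlated. Across some 14 time points, sphericity is then unlikely to hold. Without a correction, the F test for condition by time rejects too often, and a time-of-day effect of CPAP could be reported on weaker evidence than p<0.05 suggests.

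The second problem reaches the hunger hypothesis itself. The usual repeated-measures ANOVA needs every cell filled, so one skipped rating at either visit can remove the patient from all terms, including the condition effect. With about 17 completers, a few scattered gaps matter. Gaps are plausible: arrival is approximate, patients are escorted out to markets, and ratings are due only while awake in a population selected for daytime sleepiness.

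**Working it through.** **Reproducing the plan's figures.** Exact paired t-test, two-sided 0.05, noncentral t:

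- d = 0.736 needs n = 17 (power 81.3%), as stated.
- 17/(1 − 0.30) = 24.3, rounded up to 25, as stated.
- "effect size of 1.195 for decreased Stanford Sleepiness Scores (37) with 8 patients" reproduces (power 82.5%).
- "effect size of 1.01 for REM sleep increases (43) and 1.64 for SWS increases (43) with 10 and 6 patients, respectively" reproduces (81.1% and 89.0%).
- Expected completers: 25 × 0.70 = 17.5, so about 17.

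**Number of ratings.** From 0900 h to 2300 h is 14 hours, giving 14 or 15 hourly ratings per visit and 28 to 30 per patient. This is inferred from the timetable.

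**Type I error of condition by time.** With two conditions, the interaction test equals a one-way repeated-measures test on the within-patient visit differences. It was simulated under the null with n = 17, 14 ratings per visit, 8,000 runs per setting and AR(1) errors. The correlations are assumed. Uncorrected test, nominal 5%:

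| Adjacent-rating correlation | Error rate | Ratio to 5% |
|---|---|---|
| 0.3 | 5.9% | 1.2 |
| 0.5 | 8.2% | 1.6 |
| 0.7 | 11.1% | 2.2 |
| 0.85 | 13.6% | 2.7 |

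Over these settings Huynh-Feldt gives 4.9% to 6.0% and Greenhouse-Geisser 2.0% to 4.5%.

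A separate simulation with 14 or 15 ratings agrees: 6.3% to 14.4% uncorrected for correlations of 0.3 to 0.9. It gives 5.0% when ratings are independent and 5.2% under compound symmetry, so the inflation comes from the serial pattern. Rounding to an assumed 7-point scale at correlation 0.7 gives 10.1%.

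**Type I error of the condition effect.** Two conditions give 1 degree of freedom, so sphericity holds automatically. Simulated error was 4.8% to 5.6% in every setting.

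**Complete-case loss.** If each rating is missing independently with probability m, the expected number of complete patients is 17 × (1 − m)^28:

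- m = 0.5%: 17 × 0.869 = 14.8
- m = 1%: 17 × 0.755 = 12.8
- m = 2%: 17 × 0.568 = 9.7

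With 30 ratings these become 14.6, 12.6 and 9.3. At 80% power, the detectable paired effect is d = 0.72 with 17 patients and 1.00 with 10. Power for d = 0.736 falls from 81% to 55%. That effect is leptin's and serves here only as a yardstick.

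**Clustered gaps.** If the same 2% came in runs of three consecutive ratings, about exp(−28 × 0.02/3) = 0.83 of patients would stay complete: 17 × 0.83 = 14.1.

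**The case against.** A reader might infer that the plan's test of a main outcome is broken. The documents do not support that. Hypothesis 2 is about level, its test is the condition effect, and that test holds its 5%. No hypothesis in Specific Aims concerns time of day, so the inflation touches only the interaction and the time effect.

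A reader might also say that the plan prescribes an uncorrected ANOVA and the dropping of patients. It says neither. Both are the standard behaviour of the named method, inferred from silence, and many packages print corrected p-values. This stands as a limit on the claim. But a correction the plan does not name can be chosen after the results are seen, and no correction restores deleted patients.

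It is also fair that neither the correlation nor the missing rate is in the documents. At correlations of 0.3 to 0.5 the inflation is below twofold. Independent gaps are close to the worst case for complete-case loss, because they spread over the most patients. Hunger may follow self-selected meals rather than AR(1) decay. In Experimental Procedures, the hourly wording attaches directly to the energy item; hourly hunger rests on reading Statistical Procedures across to the appetite-satiety ratings. Finally, the 17 is leptin's requirement, so there is no stated power for hunger to lose. These points make the figures conditional, but they do not supply the missing rules.

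**Conclusion.** The point holds in a limited form. The plan leaves unstated both a sphericity correction and a missing-rating rule for some 28 ratings per patient, in a set of variables that includes a main outcome.

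- The hunger hypothesis keeps a type I error near 5%.
- An uncorrected interaction test would run at about 6% to 14%, or 1.2 to 2.7 times nominal, for assumed correlations of 0.3 to 0.85.
- Complete-case analysis would leave about 14.8, 12.8 or 9.7 of 17 completers at assumed independent missing rates of 0.5%, 1% or 2%, and more if gaps cluster. This loss does reach the condition effect on hunger.

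The count of 17 assumes that all 25 recruits are CPAP patients; the documents do not say whether the non-CPAP control group is included. This is an inexpensive improvement worth making, not a flaw that invalidates the hunger test.

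**What to change.** In Statistical Procedures, replace the ANOVA for these ratings with a linear mixed model on all available ratings:

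- fixed effects for condition, clock time and condition by time;
- random participant and participant-by-condition effects;
- a prespecified within-day residual covariance, for example AR(1), with a named alternative because hunger may follow meals;
- Kenward-Roger degrees of freedom.

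State that Hypothesis 2 for hunger is tested by the condition main effect and that the interaction is secondary.

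If ANOVA is kept, prespecify a Huynh-Feldt correction for time and for condition by time, because Greenhouse-Geisser is conservative at n = 17. Add an explicit rule for missing ratings.

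The cost is about a paragraph of wording and standard software, with no new data and no patient burden. The downside is that a covariance structure must be fixed in advance. The model recovers patients with partial ratings. It does not address the rule that only compliant patients have the second laboratory day.
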